## **6. ANALYSIS INTERPRETATION**

Multiple objectives and endpoints require type I error control. Full alpha (0.05) is split equally ( $\alpha=0.025$ ) between rMenB+OMV NZ objectives and MenABCWY objectives. Furthermore, within rMenB+OMV NZ, as well as within MenABCWY, objectives are tested hierarchically. If the first null hypothesis is rejected, then the testing will continue with the second hypothesis at same alpha. Same for 3rd, 4th, and so forth. Whenever a null hypothesis is not rejected, then the testing will stop.

As the comparator for MenABCWY non inferiority objective for the B component will be the selected schedule of rMenB+OMV NZ as determined in this study, the objectives of rMenB+OMV NZ will be analysed first. Additionally, if all null hypotheses related to rMenB+OMV NZ objectives will be rejected, the alpha ( $\alpha=0.025$ ) will be propagated to the MenABCWY part, and hypotheses related to MenABCWY objectives will be tested at full alpha ( $\alpha=0.05$ ). See Figure 2 for an explanation of the hierarchical testing (top to bottom, the order indicated by the arrows).

**Figure 2** Hierarchical testing of hypothesis

\* Alpha split equally between rMenB+OMV NZ and MenABCWY vaccine objectives.

If all rMenB+OMV NZ objectives achieved, MenABCWY vaccine objectives will be tested at full alpha.

\*\* If all objectives of rMenB+OMV NZ are met, the comparator will be the 0,2-months schedule. If the 0,2-months objective is not met, and the 0,6-months is met, then the 0,6-months schedule will be the comparator. If the 0,6-months is also not met, then the 0,2,6-months schedule will be the comparator.

Refer to Glossary of terms for definitions of test-based and responder-based vaccine effectiveness.

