**CONFIDENTIAL**

205416 [MENB REC 2ND GEN-038 (V72\_72)]

Statistical Analysis Plan Amendment 4

Objectives	Endpoints

subjects achieving a 4-fold rise** in hSBA titres against N. meningitidis serogroup B indicator strains is above -10%.
	

To assess the effectiveness of the rMenB+OMV NZ and MenABCWY vaccines against each of the randomly selected endemic US N. meningitidis serogroup B invasive disease strains as measured by bactericidal activity using enc-hSBA at 1 month after the 3-dose (0,2,6-months in MenB_0_2_6 group) and 2-dose (0,6-months in MenB_0_6 group, 0,2-months in MenB_0_2_6 group and 0,6-months in the ABCWY (pooled) group) vaccination series when compared to 1 month after the MenACWY vaccination.
	
The percentages of samples without bactericidal serum activity using enc-hSBA against each of the endemic US N. meningitidis serogroup B strains at 1 month after the:
 
 
3-dose vaccination series (Day 211, Month 7 in MenB_0_2_6 group)
 
2-dose vaccination series (Day 211, Month 7 in MenB_0_6 group)
 
2-dose vaccination series (Day 91, Month 3 in MenB_0_2_6 group)
 
last vaccination for the ABCWY group (pooled lots) (Day 211, Month 7), and
 
MenACWY vaccination (Day 31, Month 1 in ACWY group).
 

To describe the distribution of subjects by percentages of serogroup B invasive disease strains killed using enc-hSBA at 1 month after the 3-dose (0,2,6-months in MenB_0_2_6 group) and 2-dose (0,6-months in MenB_0_6 group, 0,2-months in MenB_0_2_6 group and 0,6-months in the ABCWY (pooled) group) vaccination series of rMenB+OMV NZ and MenABCWY vaccines.
	
The percentages of serogroup B invasive disease strains killed using enc-hSBA in each subject at 1 month after the:
 
 
3-dose vaccination series (Day 211, Month 7 in MenB_0_2_6 group)
 
2-dose vaccination series (Day 211, Month 7 in MenB_0_6 group)
 
2-dose vaccination series (Day 91, Month 3 in MenB_0_2_6 group), and
 
last vaccination for the ABCWY group (pooled lots) (Day 211, Month 7)
 

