#### **5.3.1.1. Vaccine effectiveness (Test-based): rMenB+OMV NZ - 3 doses (0,2,6-months schedule)**

Analysis set: Per-protocol set (PPS) will be the primary analysis population

Statistical method: The VE is defined as  $1 - RR = (1 - \text{percentage of samples without bactericidal serum activity at 1:4 dilution in MenB group} / \text{percentage of samples without bactericidal serum activity at 1:4 dilution in the ACWY group}) \times 100\%$  and it will be analyzed using a generalised linear model with vaccine group, strain, and randomization factors (i.e. region (US/ex-US), age category (10-17 YoA/18-25 YoA), previous MenACWY vaccination (y/n)) as independent variables. Furthermore, a repeated statement will be used to estimate the variance of the RR including correlation within subject's responses to different strains. If the statistical model does not converge due to (one of) the factor(s), a model without this/these factor(s) will be fitted instead. The response variable of the model will be the Bernoulli distributed outcome without bactericidal activity at a 1:4 dilution (i.e. response is 1 if titre  $< 4$ , and 0 if titre  $\geq 4$ ), at 1 month after the last vaccination (Month 7) in the MenB group and at Month 1 for the ACWY group. Each subject will contribute with approximately 35 measures to this analysis, each of the measures corresponding to the response variable to one of the 35 strains randomly assigned to be tested with the samples available for that specific subject.

In order to obtain the VE measure which is a measure based on the relative risk (RR), a generalised linear model will be used with the Binary distribution and link function log in order to compute the log RR and the corresponding 97.5% CI. The obtained values will be exponentiated to obtain the RR and the corresponding 97.5% CI. The VE will be computed as  $100\% \times (1 - RR)$ . Effectiveness of rMenB+OMV NZ (0,2,6-months schedule) will be demonstrated if the lower limit of the two-sided 97.5% CI for VE between MenB and the ACWY group is above 65%.

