#### 5.3.2.1. Vaccine effectiveness (Test-based): rMenB+OMV NZ - 3 doses (0,2,6-months schedule)

The SAS code to analyse the Vaccine effectiveness (Test-based): rMenB+OMV NZ - 3 doses (0,2,6-months schedule) objective is specified below. Treatment, region, age category, previous ACWY vaccination, and strains will be modelled as fixed effect. To account for a possible over-dispersion, the DSCALE option in the model statement will be evaluated first. The DSCALE will be kept in the model only if the F-statistics for the DSCALE parameter is significant ( $p<0.05$ ). The following SAS code will be used for the VE calculation:

```

ods trace on;
ods output GEEmpPEst = genmod_stats
CONVERGENCESTATUS = converge ;

PROC GENMOD data=dataset descending;
class trtgrp strain region agecat previousACWY subject_id ;
model outcome = trtgrp strain region agecat previousACWY / dist= bin
link= log DSCALE;
repeated subject = subject_id / type= CS withinsubject= strain;
estimate 'MenB026-ACWY' trtgrp 1 0 0 0 0 -1/ alpha=0.025 exp;

/*trtgrp R is MenB0,2,6 and trtgrp W is ACWY*/

run;

ods output close;

data genmod_stats;
set genmod_stats;
where parm = 'trtgrp' and level1 = '1';
rr = exp(estimate);
ub = exp(uppercl);
ve = (1 - rr)*100 ;
ve_ll = (1 - ub) * 100 ;
if ve_ll > 65 then success = 1 ;
else success = 0 ;
run;

```

where outcome represents the Bernoulli distributed outcome without bactericidal activity at a 1:4 dilution (i.e. response is 1 if titre  $< 4$ , and 0 if titre  $\geq 4$ ), one month after the 3rd vaccination in MenB 0,2,6 and one month after the MenACWY vaccination for the ACWY arm, trtgrp indicates the vaccine groups, strain is the serogroup B strain variable, region is either US or ex-US, agecat is the age at enrolment (10-17 YoA or 18-25 YoA), and previousACWY is previous ACWY vaccination (y/n) at enrolment.

rr is the relative risk (RR), which is obtained from the estimated parameters from PROC GENMOD. Vaccine effectiveness (VE) is then derived as (1-rr)x100%.

ub represents the upper bound of the 97.5% CI of the relative risk. ve\_ll is the lower bound of the 97.5% CI for VE, if the value is greater than 65%, then the Vaccine effectiveness (Test-based): rMenB+OMV NZ - 3 doses (0,2,6-months schedule) objective is successful.

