##### 5.4.2.2. Effectiveness by each of the endemic US *N. meningitidis* serogroup B strains

The SAS code to analyse the Vaccine effectiveness (Test-based): rMenB+OMV NZ - 3 doses (0,2,6-months schedule) by strain is specified below. Treatment, and randomization factors (i.e. region (US/ex-US), age category (10-17 YoA/18-25 YoA), previous MenACWY vaccination (y/n)) will be modelled as fixed effect. To account for a possible over-dispersion, the DSSCALE option in the model statement will be evaluated first. The DSSCALE will be kept in the model only if the F-statistics for the DSSCALE parameter is significant ( $p < 0.05$ ). The following SAS code will be used for the VE calculation:

```

ods trace on;
ods output GEEEmpPEst = genmod_stats
CONVERGENCESTATUS = converge ;

PROC GENMOD data=dataset descending;
class trtgrp region agecat previousACWY;
by strain ;
model outcome = trtgrp region agecat previousACWY / dist= bin link= log
DSCALE alpha=0.05;
estimate 'MenB026-ACWY' trtgrp 1 0 0 0 0 -1/ alpha= 0.05 exp;

/*trtgrp R is MenB0,2,6 and trtgrp W is ACWY*/

run;

ods output close;

data genmod_stats;
set genmod_stats;
by strain ;
where parm = 'trtgrp' and levell = '1';
rr = exp(estimate);
ub = exp(uppercl);
ve = (1 - rr)*100 ;
ve_ll = (1 - ub) * 100 ;
if ve_ll > 65 then success = 1 ;
else success = 0 ;
run;

```

where outcome represents the Bernoulli distributed outcome without bactericidal activity at a 1:4 dilution (i.e. response is 1 if titre < 4, and 0 if titre  $\geq$  4), one month after the 3rd vaccination in MenB0,2,6 and one month after the MenACWY vaccination for the ACWY arm, trtgrp indicates the vaccine groups, strain is the serogroup B strain variable, region is either US or ex-US, agecat is the age at enrolment (10-17 YoA or 18-25 YoA), and previousACWY is previous ACWY vaccination (y/n) at enrolment.

rr is the relative risk (RR), which is obtained from the estimated parameters from PROC GENMOD. Vaccine effectiveness (VE) is then derived as (1-rr)x100%.

ub represents the upper bound of the 95% CI of the relative risk. ve\_ll is the lower bound of the 95% CI for VE, if the value is greater than 65%, then the Vaccine effectiveness (Test-based): rMenB+OMV NZ - 3 doses (0,2,6-months schedule) objective is successful.

In summary in case of convergence issue the following hierarchical decision tree will be applied

- Binary model including region, agecat, and previousACWY
- Binary model, excluding region, agecat, and previousACWY

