## **6. ANALYSIS INTERPRETATION**

Multiple objectives and endpoints require type I error control. Full alpha (0.05) is split equally ( $\alpha=0.025$ ) between rMenB+OMV NZ objectives and MenABCWY objectives. Furthermore, within rMenB+OMV NZ, as well as within MenABCWY, objectives are tested hierarchically. If the first null hypothesis is rejected, then the testing will continue with the second hypothesis at same alpha. Same for 3rd, 4th, and so forth. Whenever a null hypothesis is not rejected, then the testing will stop.

As the comparator for MenABCWY non inferiority objective for the B component will be the selected schedule of rMenB+OMV NZ as determined in this study, the objectives of rMenB+OMV NZ will be analysed first. Additionally, if all null hypotheses related to rMenB+OMV NZ objectives will be rejected, the alpha ( $\alpha=0.025$ ) will be propagated to the MenABCWY part, and hypotheses related to MenABCWY objectives will be tested at full alpha ( $\alpha=0.05$ ). See Figure 2 for an explanation of the hierarchical testing (top to bottom, the order indicated by the arrows).

**Figure 2** Hierarchical testing of hypothesis

\* Alpha split equally between rMenB+OMV NZ and MenABCWY vaccine objectives.

If all rMenB+OMV NZ objectives achieved, MenABCWY vaccine objectives will be tested at full alpha.

\*\* If all objectives of rMenB+OMV NZ are met, the comparator will be the 0,2-months schedule. If the 0,2-months objective is not met, and the 0,6-months is met, then the 0,6-months schedule will be the comparator. If the 0,6-months is also not met, then the 0,2,6-months schedule will be the comparator.

Refer to Glossary of terms for definitions of test-based and responder-based vaccine effectiveness.

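### The by-strain section (5.4.2.2, SAP Amendment 4) keeps a success flag and sentence that declare the primary 0,2,6-months VE objective met on a single-strain 95% CI, contradicting 5.3.1.1, 5.3.2.1, Section 6 and Table 1

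*SAP*

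**What the plan says.** **The primary rule.** For the 0,2,6-months schedule, SAP 5.3.1.1 says effectiveness "will be demonstrated if the lower limit of the two-sided 97.5% CI for VE between MenB and the ACWY group is above 65" per cent. The population is fixed in the same section: "Analysis set: Per-protocol set (PPS) will be the primary analysis population". The model covers all strains together, with strain as a factor and a repeated statement for within-subject correlation. Section 5.3.2.1 gives the code and repeats the rule: the limit "is the lower bound of the 97.5% CI for VE, if the value is greater than 65%, then the Vaccine effectiveness (Test-based): rMenB+OMV NZ" 3-dose objective is met.

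**The hierarchy.** Section 6 states "Full alpha (0.05) is split equally" between the two vaccine families, and within each family "Whenever a null hypothesis is not rejected, then the testing will stop".

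**The by-strain objective.** Table 1 lists it as secondary: "To assess the effectiveness of the rMenB+OMV NZ and MenABCWY vaccines against each of the randomly selected endemic US" serogroup B strains. It has no criterion. Section 5.4.1.2 sets the FAS as the population and 95% as the confidence level, and restricts the analysis to pooled ABCWY and the selected MenB comparator. It gives no success rule.

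**The by-strain code and text.** Section 5.4.2.2 runs the model by strain and contains "if ve_ll > 65 then success = 1". The closing explanation then says that the limit "is the lower bound of the 95% CI for VE, if the value is greater than 65%, then the Vaccine effectiveness (Test-based): rMenB+OMV NZ" 3-dose (0,2,6-months) objective is successful. Amendments 1, 2 and 3 carry the same sentence.

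**The concern.** One named primary objective has two success rules in the same SAP. The second is looser in confidence level, works on one strain instead of all, uses a different analysis set and lies outside the alpha allocation.

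The two rules can meet at an awkward point. Under the Figure 2 footnote, the 0,2,6-months schedule becomes the comparator when the 0,6-months schedule is not met. That does not require 0,2,6 itself to have been met. The by-strain analysis of 0,2,6 could therefore be the one produced when the primary 0,2,6 objective has failed, and the sentence in 5.4.2.2 would then be available to cite.

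Nor is the by-strain result labelled descriptive. Section 5.3.2.10 shows that the SAP does this elsewhere: it says explicitly that its additional schedule comparisons carry no success criterion.

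**Working it through.** **1. The two rules side by side**

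| | 5.3.1.1 / 5.3.2.1 | 5.4.2.2 (with 5.4.1.2) |
|---|---|---|
| Objective named | Test-based VE, 0,2,6-months | The same title |
| Strains | All, one model | One at a time |
| Confidence level | 97.5% | 95% |
| Analysis set | PPS | FAS |
| Threshold for the lower limit | 65% | 65% |
| ESTIMATE contrast | MenB 0,2,6 minus ACWY | The same |
| Place in the Section 6 hierarchy | Yes | No |

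**2. The plan's own alpha.** 0.025 + 0.025 = 0.05, as Section 6 states. A two-sided 97.5% CI has one-sided error 0.025 / 2 = 0.0125, so the primary rule allows a 1.25% chance of false success on this objective.

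**3. Worst-case size of the by-strain rule.** Inputs from the SAP: 110 strains and a 95% CI, hence 0.025 one-sided per strain. Assumptions not in the SAP: true VE is exactly 65% on every strain, and any one strain passing counts as success.

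- Independent strains: 1 − 0.975^110 = 0.938, about 94%. The expected number of strains passing is 110 × 0.025 = 2.75.
- Equicorrelated test statistics (Monte Carlo): about 70% at correlation 0.2, 41% at 0.5 and 18% at 0.8.

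**4. Closer to the design.** With about 35 of 110 strains tested per subject, the results per strain are 684 × 35 / 110 ≈ 218 in the MenB group and 137 × 35 / 110 ≈ 44 in the ACWY group. The share of ACWY samples not killed is not in the SAP, so it was assumed.

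- Exact per-strain error of a Wald log-RR interval, with that share from 0.95 down to 0.5: 1.9% to 2.8%. Under independence this gives 87% to 96% over 110 strains.
- Simulations with shared subjects (latent within-subject correlation 0.2 to 0.5; share not killed 0.7 or 0.9): about 77% to 89%.

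**5. Strains that differ.** With strain VEs spread evenly from 30% to 90% (mean 60%, below the criterion) and latent correlation 0.2, at least one strain passed in each of 200 simulated trials, about 28 to 32 strains on average. Many of those passes are true for the strain concerned. A strain-level pass therefore says little about the all-strain objective.

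**The case against.** **The controlling sections are clear.** Sections 5.3.1.1, 5.3.2.1 and 6 fix the primary decision. Section 5.4.2.2 sits under a secondary heading and introduces its code as being by strain. The flag and sentence look like residue from 5.3.2.1. The code supports this: the DATA step reads the GEE parameter table, which PROC GENMOD creates only with a REPEATED statement, and the by-strain call has none. This stands. A reader might infer that the sponsor means to claim primary success through single strains, or that the run would yield 110 success flags for every schedule. The documents support neither: the code as printed would not fill the flag, and 5.4.1.2 limits the analysis to pooled ABCWY and one selected comparator.

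**95% is the intended by-strain level.** This also stands. Section 5.4.1.2 sets it deliberately for those estimates. It is wrong only for the primary objective that the sentence names.

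**The treatment contrast is unchanged.** Correct. The ESTIMATE coefficients match in both sections; the strain scope, confidence level and analysis set are what differ.

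**The error rates rest on an unstated rule.** Correct. The SAP never says how many strains must pass, and the design-based figures need an assumed control rate. They are worst-case figures.

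**The text may be superseded.** Amendment 5 exists, but the part at hand begins after its 5.4.2.2. Repetition through Amendments 1 to 4 shows persistence, not the current wording.

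None of this removes the contradiction in the text at hand. A copied sentence in an SAP remains a prespecified statement until it is corrected.

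**Conclusion.** In Amendment 4, and in Amendments 1 to 3, Section 5.4.2.2 states a success rule for the primary 0,2,6-months test-based objective that conflicts with 5.3.1.1, 5.3.2.1, Section 6 and Table 1. It should be corrected. It does not show that the primary analysis itself is misdesigned.

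If the sentence were applied on the any-one-strain reading, with VE of 65% throughout, false success would be far more likely than the 1.25% allowed: about 94% under independence, about 77% to 89% in simulations with shared subjects, and still about 18% at a test-statistic correlation of 0.8. These figures depend on that reading, on a common VE at the threshold and, for the simulations, on an assumed control not-killed rate. Confidence about the current SAP is limited because Amendment 5's version of the section could not be read.

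**What to change.** First check whether 5.4.2.2 in Amendment 5 still contains the text. If it does:

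- Delete the success flag from the by-strain DATA step.
- Delete the sentence declaring the 0,2,6-months objective successful.
- Add a statement such as: By-strain VE is descriptive; point estimates and nominal 95% CIs are presented without a success criterion. The primary test-based objective is decided only by the all-strain model of 5.3.1.1 and 5.3.2.1 at the confidence level given there.

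The cost is a few lines of SAP text and code. The by-strain estimates and their 95% intervals are still reported, and neither the data nor the sample size nor the primary analysis changes. Only the strain-level success labels are lost.

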**5.4.2.3. Distribution of percentages of serogroup B invasive disease strains killed**

Not applicable

**5.4.2.4. Immune response of MenABCWY, rMenB+OMV NZ and MenACWY**

Not applicable

**5.5. Safety and reactogenicity**

**5.5.1. Analysis of safety and reactogenicity planned in the protocol**

Distribution of subjects by vaccinations will be summarised by vaccine group for the Enrolled Set. In case of vaccination error, subjects will be analyzed “as treated” (according to the vaccine the subject received).

**Analysis sets:** Solicited Safety Set (solicited local and systemic adverse events and other solicited adverse events), Unsolicited Safety Set (unsolicited adverse events), and Overall Safety Set.

## CONFIDENTIAL

205416 [MENB REC 2ND GEN-038 (V72\_72)]

Statistical Analysis Plan Amendment 4

Endpoint	Statistical Analysis Methods
Primary	
Endpoints description: The frequencies and percentages of subjects with solicited local (i.e., injection site pain, erythema, swelling, induration) and systemic (i.e., fever [temperature <math>\geq 38.0^{\circ}\text{C}</math>], nausea, fatigue, myalgia, arthralgia, headache) adverse events during the 7 days (including the day of vaccination) following each vaccination at Day 1, Day 61 and Day 181.
 
All solicited adverse events will be summarised according to defined severity grading scales, see protocol section 12.5.9.3.
 
Frequencies and percentages of subjects experiencing each adverse event will be presented for each symptom severity. Summary tables showing the occurrence of any local or systemic adverse event overall and at each time point will also be presented.
 
Post-vaccination solicited adverse events reported from Day 1 to Day 7 will be summarised for the intervals Day 1-3, Day 4-7, and Day 1-7 by maximal severity and by vaccine group, excluding the 30-minute measurement, which will be summarised separately. The severity of solicited local adverse events, including redness (erythema) at injection site, swelling of skin at injection site, and hardness of skin at injection site will be summarised according to categories based on linear measurement: None (1 to 24mm); Mild (25 to 50mm); Moderate (51 to 100mm); Severe (<math>>100\text{mm}</math>).
 
Injection site tenderness and systemic reactions (except fever) occurring up to 7 days after each vaccination at Day 1, Day 61 and Day 181 will be summarised according to "mild", "moderate" or "severe".
 
Each solicited local and systemic adverse event will also be further summarised as "none" versus "any" (for fever the latter will be <math>\geq 38.0^{\circ}\text{C}</math>).
 
Use of antipyretics and analgesics will be summarised by frequency by type of use (prophylactic versus treatment) and percentage of subjects reporting use.
 
Body temperature will be summarised by <math>0.5^{\circ}\text{C}</math> increments from <math>36.0^{\circ}\text{C}</math> up to <math>\geq 40^{\circ}\text{C}</math> and will be broken down according by route of measurement, if applicable. Frequencies and percentages of subjects with temperatures <math>\geq 38.0^{\circ}\text{C}</math> and temperatures <math>\geq 40.0^{\circ}\text{C}</math> will also be presented.

	
Endpoints description: The frequencies and percentages of subjects with any unsolicited AEs (including all SAEs), AEs leading to withdrawal and medically attended AEs during the 7 and the 30 days (including the day of vaccination) following each vaccination at Day 1, Day 61 and Day 181.
 
The frequencies and percentages of subjects with SAEs, AEs leading to withdrawal, AESIs and medically attended AEs throughout the study period.
 
This analysis applies to all adverse events occurring during the study, judged either as possibly related, or not related to vaccination by the investigator, recorded in AE CRF, with a start date on or after the date of first vaccination. AE starting prior to the first vaccination will only be listed.
 
The original verbatim terms used by investigators to identify adverse events in the CRFs will be mapped to preferred terms using the MedDRA dictionary. The adverse events will then be grouped by MedDRA preferred terms into frequency tables according to system organ class.
 
All reported adverse events, as well as adverse events judged by the investigator as possibly related to study vaccine, will be summarised according to system organ class and preferred term within system organ class. These summaries will be presented by vaccine group and by interval of study observation. When an adverse event occurs more than once for a subject, the maximal severity and strongest relationship to the vaccine group will be counted.
 
Separate summaries will be produced for the following categories:
 
 
• Serious adverse events.
 
• Adverse events that are possibly related to vaccine.
 
• Adverse events of special interest.
 
• Adverse event leading to withdrawal.
 
• Adverse events leading to a medically attended visit.
 
 
Data listings of all adverse events will be provided by subject. In addition, adverse events in the categories above will be provided as listed data.
 
Local and systemic AEs will be analyzed by point estimates with associated 95% CIs [Clopper, 1934].

